### **8.4.2 Concomitant Medications**

Concomitant medications taken during the study will be listed.

### **8.4.3 RCL Testing**

Number (%) of subjects testing positive for RCL will be summarised for each of the IMP treated groups by visit and at any time.

### **8.4.4 Laboratory Evaluations**

#### **8.4.4.1 Haematology**

Haematology parameters (red blood cell (RBC) count, haemoglobin, haematocrit, mean corpuscular volume (MCV), mean corpuscular haemoglobin (MCH), mean corpuscular haemoglobin concentration (MCHC), white blood cell (WBC), neutrophils, lymphocytes,

monocytes, eosinophils, basophils and platelet count) will be evaluated over time for the IMP treated subjects. The baseline evaluation for each parameter will be the final evaluation prior to the IMP infusion.

For each parameter, the actual value and change from baseline will be summarised at each visit using descriptive statistics for each of the IMP treated groups.

Haematology evaluations will be flagged against the normal range as low/normal/high. For each parameter, the number (%) of subjects with evaluations that were low/normal/high relative to the normal range will be summarised by visit. In addition, shift tables will be constructed comparing the flags at the baseline evaluation with those at each post-infusion evaluation and the minimum and maximum evaluation post-infusion. Out of range values will be assessed for their clinical significance. The number (%) of subjects with any clinically significant abnormal values will be summarized by parameter at each visit and at any time post-infusion.

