#### **4.2.2 Secondary objectives**

The secondary objectives are to:

- Compare survival and event free survival at 2 and 3 years between patients treated with IMP and patients treated with allogeneic HSCT
- Determine the percentage of IMP treated patients requiring immunoglobulin replacement therapy at all evaluation points from 18 months onwards
- Compare frequency of infections, and growth of pathogenic microorganisms over 3 years
- Evaluate the longitudinal clinical effect in terms of improved immunity
- Evaluate tolerability of conditioning regimen. These data will be reviewed and interpreted by the PI and the study team
- Evaluate feasibility of the transduction procedure. These data will be reviewed and interpreted by the PI and the study team

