### **5.4 Concomitant medication**

Entry into this study will not affect concomitant treatments for ADA-deficiency, such as prophylactic antibiotics or intravenous gamma globulin therapy. However, the patient will be

withdrawn from cotrimoxazole prophylaxis at least day -1 prior to IMP infusion. Cotrimoxazole will be restarted when ANC > 1 x 10^9/l on 3 consecutive days after reinfusion of transduced cells. Aerosolised or intravenous pentamidine will be used as prophylaxis for *Pneumocystis jirovecii* in the intervening time period.

PEG-ADA will be continued until one month (+/- 6 days) post-infusion of gene-modified cells. PEG-ADA will be restarted if i) the child is withdrawn from the study ii) if after 180 days there is no evidence of gene modified cell engraftment and/or failure of T cell recovery.

PEG-ADA may be restarted at PIs discretion prior to this time point on clinical grounds e.g infective problems or delayed T cell reconstitution.

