### **8.2.2 Post-infusion monitoring**

Patients will be monitored on protocol at 1 month, 6 weeks, 3, 6, 9, 12, 18, 24, 30 and 36 months post-infusion. Window to carry out these visits is +/- 5 days for visits at 1 month, 6 weeks and +/- 2 weeks for visits at 3, 6, 9, 12, 18, 24, 30 and 36 months. Follow-up as part of the routine clinical care of post-transplant patients will be annual after this.

Monitoring, testing being performed and information to be collected on CRF are fully detailed in Appendix 5. Modifications to this protocol will be adopted as necessary to improve sample-processing capability, and a degree of flexibility regarding the actual dates of assessment will be maintained. Additional tests may be carried out in the event of a significant adverse effect to ensure optimal clinical care.

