Vital Signs	Patient's weight Temperature Heart rate Respiratory rate Oxygen saturation	X	X	X	X	X	X	X	X	X	X	X	X
Physical examination	Cardiovascular system Respiratory system Ear, Nose, Throat, Neck and Eyes (only at PreGT, 36 m) Neurological System (only at PreGT, 36 months) Abdominal Skin Other	X		X	X	X	X	X	X	X	X	X	X
Infection status	Evaluate any active infection at time of visit (respiratory tract, meningitis, sepsis, skin and mucosa, ear, nose and throat, abscess, persistent fever, other) Evaluate if there is any infection resulting in hospitalisation since last visit	X		X	X	X	X	X	X	X	X	X	X
PEG-ADA ERT status	Confirmation that if PEG-ADA has been administered or not since last visit	X		X	X	X	X	X	X	X	X	X	X
Blood Count	Haemoglobin, Platelet count White cell count Neutrophil count Lymphocyte count	X		X	X	X	X	X	X	X	X	X	X

Assessment	Result to be reported on the CRF	PreGT	Treatment	1	1.5	3	6	9	12	18	24	30	36
Lymphocyte subset counts	CD 3 CD19 CD16+ CD 56+ CD3+ CD4+ CD3+ CD8+ Naïve: CD4+CD45RA+CD27+	X		X	X	X	X	X	X	X	X	X	X
T cell function PHA stimulation**	Normal/Abnormal	X				X	X		X	X	X		
Lymphocyte function CD3 stimulation**	Normal/Abnormal								X			X	
GAM ***	Ig G level Ig A level Ig M level Immunoglobulin status since last visit	X						X	X	X	X	X	X
TRECS	TRECS on T cells TRECS on MNCs	X						X		X		X	
Vβ Spectratyping	Reported as Normal/Abnormal							X		X	X	X	X
Vector copy number in cells (qPCR)	vector copy number in PBMC vector copy number in CD34 vector copy number in CD3 vector copy number in CD19 vector copy number in myeloid							X	X	X			X
Integration analysis	Normal/Abnormal						X****	X****		X		X****	X
Tetanus vaccination responses	Normal/Abnormal											X	X
ADA metabolite analysis (dATP) and ADA activity	Plasma deoxyadenosine level ADA (rbc) level dATP level	X		X	X	X	X	X	X	X	X	X	X
RCL (blood)	Reported as detectable / not detectable	X				X****	X****		X		X****		X

Assessment	Result to be reported on the CRF	PreGT	Treatment	1	1.5	3	6	9	12	18	24	30	36
------------	----------------------------------	-------	-----------	---	-----	---	---	---	----	----	----	----	----

Bone marrow aspirate for vector copy number qPCR and integration analysis (optional)	Morphology (Normal/ Abnormal) Vector copy number in BM-MNC Integration analysis (Normal / Abnormal)								X		X		X
Immunology save serum & SCLN (stored cells)	Serum collection date SCLN s collection date	X						X		X	X	X	X
Reporting of Adverse Event			X	X	X	X	X	X	X	X	X	X	X

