Reporting of Concomitant Treatment ^^			X	X	X	X	X	X	X	X	X	X	X

\*Lab results to be entered into eCRF for these time points should be the ones closer to the consent date/ visit date

^^ Concomitant reporting: In case of any change in administering a concomitant medication i.e. dose, frequency etc. the previous medication should be stopped where the new medication has started

\* Assay to be performed only if patient > 12 years of age

\*\* Assay can only be performed if the lymphocyte count > 0.5 x 10^9/L

# Assay to be carried out until evidence of T cell recovery

\*\*\* Pre-gene therapy assay should be carried out only if not already done at diagnosis

\*\*\*\* Sample are stored but analysed retrospectively only in case sample at 1 year visit or 3 year visit are positive

**PHA** - phytohaemagglutinin stimulation, **Ig** – immunoglobulin, **TCR** - T cell receptor, **RCL** - replication competent lentivirus, **TREC** - TCR excision circles, **PCR** - polymerase chain reaction, **SCLN** - save cells in liquid nitrogen

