#### ***Blood and the lymphatic system disorders:***

Myelo-suppression and immuno-suppression were the desired therapeutic effects of the conditioning regimen. Therefore all patients experienced profound cytopenia: leukopenia 96%, thrombocytopenia 94% and anemia 88%. The median time to neutropenia was 4 days for both autologous and allogeneic patients. The median duration of neutropenia was 6 days and 9 days for autologous and allogeneic patients.

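### No blood count or liver test is scheduled for the eCRF between infusion and month 1, and the SAP has no rule for unscheduled results, so its post-infusion minimum and maximum tables cannot be relied on to contain acute conditioning toxicity.

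*SAP*

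**What the plan says.** Protocol 8.2.2 sets the visits: "Patients will be monitored on protocol at 1 month, 6 weeks, 3, 6, 9, 12, 18, 24, 30 and 36 months post-infusion". It adds: "Window to carry out these visits is +/- 5 days for visits at 1 month, 6 weeks".

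The schedule in Protocol Appendix 5 is repeated in SAP section 3. The blood count row ("Haemoglobin, Platelet count White cell count Neutrophil count Lymphocyte count") is marked before gene therapy, blank in the treatment column, and marked again from month 1. The biochemistry row, which holds ALT, GGT and bilirubin, follows the same pattern. Vital signs and adverse event reporting are marked at treatment, so that column is used where data are wanted. A footnote on the timepoints says: "Lab results to be entered into eCRF for these time points should be the ones closer to the consent date/ visit date".

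SAP 8.4.4.1 (haematology) and 8.4.4.2 (biochemistry) take these data and plan that "shift tables will be constructed comparing the flags at the baseline evaluation with those at each post-infusion evaluation and the minimum and maximum evaluation post-infusion". They also count subjects with clinically significant abnormal values at any time after infusion. Neither section mentions unscheduled or inpatient results.

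Protocol 4.2.2 and SAP 4.2 include among the secondary objectives: "Evaluate tolerability of conditioning regimen". Both assign the review to the principal investigator and study team. SAP 5.2 lists no endpoint for it, and SAP 8.2.13 summarises only who was conditioned, body size, busulfan dose and AUC.

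**The concern.** A reader of a shift table to the post-infusion minimum will take it to show how low the counts went. If the data behind it start at month 1, it shows how low they were once the first weeks had passed. A child with normal neutrophils at baseline, a deep but short neutropenia after busulfan and recovery before month 1 would appear as normal to normal. The same applies to the maximum ALT, GGT and bilirubin.

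This matters more here because acute toxicity is an open question. Protocol 3.6 says the busulfan dosing differs from earlier studies and is intended to give more myeloablation. Protocol 9.1.3 says the toxicity of low-dose busulfan in children is not known. Protocol 8.2.3 names laboratory assessments as one of three sources for the safety summary. For the weeks when conditioning toxicity is most likely, that source has nothing scheduled.

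**Working it through.** The documents state no figure on this point to reproduce. The check is calendar arithmetic on the schedule and the label extract.

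**First scheduled draw, counted from infusion**
- Month length as in the SAP: 365.25 / 12 = 30.4 days. Month 1 with its 5-day window is day 25.4 to 35.4.
- With a 28-day month it is day 23 to 33.
- Week 6 is 42 ± 5, that is day 37 to 47.
- Of the 10 scheduled post-infusion visits, none falls before day 23.

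**Label timing of neutropenia** (Protocol Appendix 6, adult data, n = 103)
- Median time to onset is 4 days. For duration: "The median duration of neutropenia was 6 days and 9 days for autologous and allogeneic patients".
- Onset plus duration: 4 + 6 = day 10 (autologous); 4 + 9 = day 13 (allogeneic). Adding two medians is only a guide.

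| Month length | Earliest draw | Gap after day 10 | Gap after day 13 |
|---|---|---|---|
| 30.4 days | 25.4 | 15.4 days | 12.4 days |
| 28 days | 23 | 13 days | 10 days |

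The gap is about 10 to 15 days. The extract does not say which day is day 0. If it counts from busulfan, which Protocol 7.5.6 places at least 24 hours before infusion, the gap is longer.

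**If the nadir here is later or longer**

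The documents give no timing for this regimen, so I assumed onset on day 4, 10, 14 or 18 and duration of 6, 9, 14 or 21 days. The 16 end days are:

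| Onset | 6 days | 9 days | 14 days | 21 days |
|---|---|---|---|---|
| Day 4 | 10 | 13 | 18 | 25 |
| Day 10 | 16 | 19 | 24 | 31 |
| Day 14 | 20 | 23 | 28 | 35 |
| Day 18 | 24 | 27 | 32 | 39 |

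Against a draw on day 25.4, neutropenia has ended in 10 of the 16 combinations and is still present in 6. These are counts of scenarios, not probabilities. A count that is still low on that day need not be the lowest one.

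**Liver tests**

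Appendix 6 reports grade 3 transaminases in 24% of 55 children but gives no timing, so no gap can be calculated. What can be said is that no ALT, GGT or bilirubin value is scheduled before month 1.

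**The case against.** The strongest reply is that the early period is not unobserved.

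- Protocol 11.2 puts all adverse events on the eCRF, graded on the WHO scale in Appendix 7, which covers neutrophils, platelets, ALT, GGT and bilirubin. Reporting starts at treatment, and SAP 8.4.1.2 tabulates events by maximum severity. Marrow aplasia beyond 1 month is a named serious event.
- Counts are clearly taken on the ward. Protocol 5.4 restarts cotrimoxazole on a neutrophil level held "on 3 consecutive days after reinfusion of transduced cells", and Protocol 4.1 has a 6-week marrow recovery rule.
- Protocol 8.2.2 allows additional tests, and Protocol 8.2.3 says safety is analysed continuously on the data available. The footnote governs which result is used for a timepoint and does not bar other entries. SAP 8.4.4 also lists parameters that are not in the schedule rows (red cell indices and AST, for example), so the schedule may not show everything on the eCRF.

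Much of this stands, and it rules out three stronger readings. A reader might infer that no count is recorded before month 1; the documents show only that none is scheduled for the eCRF. A reader might infer that the nadir is certainly missed; that rests on adult medians from another regimen with day 0 unstated. A reader might infer that the tolerability objective will receive a falsely clean result; neither document ties that objective to these tables.

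The reply does not close the gap. Under Protocol 11.2, recording a significant laboratory abnormality as an adverse event is optional, and Appendix 6 describes myelosuppression as an intended effect, so reporting may be uneven. Under SAP 8.4.1, events between busulfan and infusion are listed but not summarised. Adverse event tables do not give the depth of a nadir or the days to recovery. Leaving room for unscheduled values is not a rule for using them.

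The biochemistry row is garbled in the text I worked from: 12 marks follow the treatment column for 10 visits. The blank at treatment and the restart at month 1 are legible, and the visit list in Protocol 8.2.2 contains nothing earlier.

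**Conclusion.** The point holds in this form. On scheduled data, the SAP's minimum and maximum shift tables and its any-time counts contain nothing from roughly the first three and a half weeks after infusion (25.4 / 7 = 3.6 weeks; 3.3 with a 28-day month). They are uninformative about the acute period and can look clean.

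If the adult label medians applied, neutropenia would be over about 10 to 15 days before the first scheduled count. That size is an assumption. With a later or longer nadir, month 1 or week 6 would catch part of it, though not reliably its depth or duration. For liver tests the gap in the schedule is established, but the timing of any peak is not.

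The conclusion assumes that the eCRF follows the schedule and that no SAP rule admits other values; the eCRF itself is not among the documents. The change should be made: it is cheap, and the plan as written does not deliver what its table titles promise.

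**What to change.** 1. Enter on the eCRF the blood counts and liver tests already taken in routine care from start of conditioning to month 1. The minimum set is the lowest neutrophil and platelet counts and the highest ALT, GGT and bilirubin, each with its date.
2. State in SAP 8.4.4 that unscheduled and inpatient values count toward the minimum, maximum and any-time summaries. The by-visit summaries can keep the result closest to the visit.
3. Adjust the baseline at the same time. SAP 8.4.4 uses the last value before infusion, so once ward results are entered it would pick up a count taken after busulfan. Define baseline for these tables as the last value before conditioning, and say whether the extremes run from conditioning or from infusion.
4. Report descriptively the lowest and highest values, their WHO grade, and the time to neutrophil and platelet recovery. Fix the recovery definition in the SAP as a reporting convention only. The levels in Protocol 4.1 (neutrophils 0.5 and platelets 20 × 10⁹/L) could serve. The three-day condition in Protocol 5.4 belongs to a different rule with a different neutrophil level (1 × 10⁹/L), so a combination of the two should not be presented as the protocol's own.
5. If the results cannot be entered, label the tables as scheduled visits from month 1 only.

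The cost is modest retrospective data entry for about 10 on-study children plus the compassionate-use group, and a few SAP sentences. Protocol 5.4 shows that serial neutrophil counts should exist. That platelets and liver tests can be recovered from ward records without new draws is an assumption to confirm with the site.

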#### **8.4.4.2 Biochemistry**

Biochemistry parameters (sodium, glucose, chloride, potassium, urea, creatinine, calcium, magnesium, phosphates, albumin, alkaline phosphatase, alanine transaminase (ALT), aspartate transaminase (AST), gamma glutamyl transferase (GGT), bilirubin, total protein) will be evaluated over time for the IMP treated subjects. The baseline evaluation for each parameter will be the final evaluation prior to the IMP infusion.

For each parameter, the actual value and change from baseline will be summarised for each IMP treated group at each visit using descriptive statistics.

Biochemistry evaluations will be flagged against the normal range as low/normal/high. For each parameter, the number (%) of subjects with evaluations that were low/normal/high relative to the normal range will be summarised by visit. In addition, shift tables will be constructed comparing the flags at the baseline evaluation with those at each post-infusion evaluation and with the minimum and maximum evaluation post-infusion. Out of range values will be assessed for their clinical significance. The number (%) of subjects with clinically significant abnormal values will be summarized by parameter at each visit and at any time post-infusion.

#### **8.4.5 Vital Signs and Weight**

Vital signs (temperature, pulse rate, respiratory rate, oxygen saturation) and weight are measured over time for the IMP treated subjects.

The baseline evaluation for each of the vital signs and weight will be the final evaluation prior to the IMP infusion.

For each parameter, the actual value and change from baseline will be summarised for each of the IMP treated groups at each visit using descriptive statistics.

Each subject's vital signs be categorized as normal, abnormal not clinically significant or abnormal clinically significant at each visit. The number (%) of subjects with clinically significant evaluations will be summarised for each parameter by visit and at any time post-infusion. In addition, the number (%) of subjects requiring additional O2 will be summarised by visit.

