#### 5.1.1 Inclusion criteria

1. Diagnosis of ADA-SCID confirmed by DNA sequencing OR by confirmed absence of <3% of ADA enzymatic activity in peripheral blood or (for neonates) in umbilical cord blood erythrocytes and/or leucocytes or in cultured foetal cells derived from either chorionic villus biopsy or amniocentesis, prior to institution of PEG-ADA replacement therapy
2. Patients who lack a fully HLA-matched family donor
3. Patients (male or female) < 5years of age OR  
  
Patients (male or female) ≥ 5years to 15rs of age who have preserved thymic function as evidenced by presence of >10 % naïve T cells (CD4+45RA+27+ cells)
4. Parental/guardian signed informed consent

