#### Safety

- To assess clinical, haematological and immunological progress of subjects
- To assess vector integration sites and clonal proliferation. This analysis will be performed at a specialised laboratory in Germany and the data will be reviewed and interpreted by the Principal Investigator (PI) and the study team

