## 7 Analysis Populations

### 7.1 Efficacy Population

#### IMP Treated Subjects

The study protocol recruited 10 subjects with a diagnosis of ADA-SCID to be treated with IMP at GOSH. These subjects will be known as the “on-study” subjects.

In addition, a group of subjects were treated under a Compassionate Use Programme (CUP under GOSH Special License) either because the study was not yet open and urgent treatment was needed, because they were outside of the inclusion/exclusion criteria or because they followed a different process (i.e., received the IMP in two infusions). These subjects followed the same study schedule as the on-study subjects.

The primary efficacy population for analysis will consist of the on-study IMP treated subjects. A secondary efficacy population will consist of all IMP treated subjects (on-study and CUP)

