### **8.4.6 Physical Examination**

Physical examinations will be performed over time for the IMP treated subjects. The number (%) of subjects with abnormal evaluations will be summarized by body system for each of the IMP treated groups at each visit. An overall summary will also be produced for each body system showing the number (%) of subjects with normal evaluations at screening who had one or more abnormal evaluations post-treatment.

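### SAP 8.4.5 summarises weight only as raw value and raw change by visit, so in growing children that table cannot by itself show whether weight gain is as expected

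*SAP*

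**What the plan says.** SAP 8.4.5 opens: "Vital signs (temperature, pulse rate, respiratory rate, oxygen saturation) and weight are measured over time for the IMP treated subjects". Baseline is the last measurement before infusion. The rule given for all of these measures, weight included, is that "the actual value and change from baseline will be summarised for each of the IMP treated groups at each visit using descriptive statistics". The general rules in SAP section 8 make those statistics the mean, standard deviation, median, minimum, maximum and number of subjects. They are given for on-study subjects and for on-study plus CUP subjects together.

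The same section sorts vital signs into normal, abnormal without clinical significance and abnormal with clinical significance. Its opening sentence lists the vital signs without weight. The study schedule (SAP section 3, Protocol Appendix 5), however, places weight in the Vital Signs row, and the clinically significant findings are counted for each parameter. Whether the categories cover weight is left open.

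Other measures are given a reference:
- SAP 8.4.4.1: "Haematology evaluations will be flagged against the normal range as low/normal/high", with shift tables.
- SAP 8.4.4.2: "Biochemistry evaluations will be flagged against the normal range as low/normal/high", with shift tables.
- SAP 8.3.1.4 and 8.3.2.2: individual plots of lymphocyte subsets and immunoglobulins carry site-supplied normal ranges that depend on age.

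No growth reference for weight appears in either document.

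**The concern.** A weight table in kilograms is easy to read for adults, whose expected change is near zero. In children the expected change is not zero, and it depends on age at entry and on sex. Protocol 5.1.1 admits children from birth to 15 years. CUP children were treated off trial in part "because they were outside of the inclusion/exclusion criteria or because they followed a different process" (SAP 7.1), so their ages may be wider still, and they are pooled with on-study children in one of the two summary groups. A mean change in kilograms therefore mixes ordinary growth at different ages with any effect of disease or treatment.

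This bears on interpretation because one stated safety objective is "To assess clinical, haematological and immunological progress of subjects" (SAP 4.1), and the protocol (3.1 and 3.1.4.1) names failure to thrive among the common manifestations of the disease. Weight is already collected before treatment, at treatment and at every follow-up visit. What is at stake is whether that series can be read as growth that is kept, regained or lost.

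**Working it through.** The plan attaches no figure to this point, so there is nothing to reproduce. The check has a textual part and an illustration.

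**Text.** Protocol 5.1.1 sets entry at under 5 years, or 5 to 15 years with preserved thymic function. Follow-up is 3 years after infusion (Protocol section 2). The oldest on-study child could therefore be 15 + 3 = 18 at the last visit, and the youngest a newborn at entry. SAP 8.4.5 uses one summary in kilograms for all of them. The text alone establishes the point.

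**Illustration.** The documents give no growth figures, so every input here is assumed, and the inputs describe small children only:
- baseline weight W0 = 8 or 12 kg, on the reference median (z = 0);
- expected gain g = 2 or 3 kg per year;
- one z-score = a share c of expected weight, with c = 0.10 or 0.15.

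Formulas: expected weight at month 36 is W36 = W0 + 3g; expected gain is 3g; shortfall for a fall of 1 z-score is c × W36; share of expected gain kept is (3g − c × W36) / 3g.

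| W0 | g | c | W36 | Expected gain | Shortfall | Observed gain | Share kept |
|---|---|---|---|---|---|---|---|
| 8 | 2 | 0.10 | 14 | 6 | 1.40 | 4.60 | 77% |
| 8 | 2 | 0.15 | 14 | 6 | 2.10 | 3.90 | 65% |
| 8 | 3 | 0.10 | 17 | 9 | 1.70 | 7.30 | 81% |
| 8 | 3 | 0.15 | 17 | 9 | 2.55 | 6.45 | 72% |
| 12 | 2 | 0.10 | 18 | 6 | 1.80 | 4.20 | 70% |
| 12 | 2 | 0.15 | 18 | 6 | 2.70 | 3.30 | 55% |
| 12 | 3 | 0.10 | 21 | 9 | 2.10 | 6.90 | 77% |
| 12 | 3 | 0.15 | 21 | 9 | 3.15 | 5.85 | 65% |

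The raw change is a gain in every row, at 55% to 81% of what was expected. The z-score change is −1 in every row.

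**Cross-check with a larger fall.** Assume baseline weight 5, 8, 12 or 18 kg, an expected 36-month gain G of 6, 8 or 10 kg, and a coefficient of variation CV of weight for age of 0.10, 0.12 or 0.14. A child who goes from the median to z = −2 ends at (W0 + G) × exp(−2 × CV). The raw change is positive in all 36 combinations. The smallest is 24 × exp(−0.28) − 18 = 18.14 − 18 = +0.14 kg, and the largest is 15 × exp(−0.20) − 5 = 12.28 − 5 = +7.28 kg. The lower end is close to zero, so harsher inputs could give a loss. Within these ranges, a positive raw change does not separate normal from faltering growth.

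**The case against.** The strongest reply is that this is presentation rather than error. Growth is neither an objective nor an endpoint. The objective on clinical progress is general, and weight is summarised as routine descriptive safety data. Any raw paediatric weight table has this limit. That stands, and it is why the point is minor.

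Other routes exist. Clinically significant abnormal test results may be recorded as adverse events (Protocol 11.2), which are tabulated (SAP 8.4.1.2). SAP 8.4.6 counts children whose "abnormal evaluations will be summarized by body system for each of the IMP treated groups at each visit". Protocol 8.9.2 provides by-subject listings as appropriate, and with 10 on-study children the individual weights could be read one by one. The clinical-significance categories may also cover weight. These routes are real but partial. The toxicity scale in Protocol Appendix 7 has no weight or growth item, the examination list has none beyond an open category, and no age standard for judging weight is named.

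Two recorded decisions also matter. SAP 10.2 removed tables of reference ranges so that current site ranges could be used, so the lack of a printed standard is partly the SAP's convention. That convention explains where ranges are kept. It does not supply one for weight, because 8.4.5 does not say that weight is compared with any range. SAP 10.1 removed plots of vital signs over time as not useful. Whether that included weight is not stated, but it is a reason to prefer a listing to new plots. Finally, the haematology and biochemistry sections refer to a normal range without calling it age-specific. The closer precedent is the age-dependent ranges for lymphocyte subsets and immunoglobulins.

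A reader might infer that the plan would miss faltering growth altogether. The documents do not support that, because the routes above remain open.

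**Conclusion.** The point holds as a minor one. The weight summary stated in SAP 8.4.5 is raw value and raw change by visit, and with these ages and this follow-up that table cannot by itself show whether weight gain is as expected. This rests on the text and does not depend on the illustration. The figure of 55% to 81% rests wholly on assumed inputs for small children and is not an estimate for this trial.

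A reader might also infer that the safety objective fails, or that an efficacy conclusion is at risk. Neither follows. No primary or secondary endpoint uses weight, and weight is summarised for gene-therapy subjects only, so no comparison with transplant changes. Nor do the documents give the ages or weights of the treated children, so no figure is offered for how far a group mean could mislead.

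**What to change.** In SAP 8.4.5:
- Keep the raw weight summary.
- Add weight-for-age z-score and its change from baseline, by visit, for each gene-therapy group. Use one named age- and sex-specific reference that covers birth to 18 years and the actual CUP ages.
- Add a listing of subjects whose z-score falls by 1 or more from baseline. The child in the illustration, who falls by exactly 1, would then be listed.
- State whether the clinical-significance categories apply to weight.

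The cost is SAP wording, one derivation and the choice of a reference suited to a cohort referred from centres worldwide (Protocol 5.1). No new assessment is needed: weight is on the schedule, and date of birth is already used for on-study and CUP subjects (SAP 8.2.2, 8.2.14). Sex must be confirmed for CUP subjects, because SAP 8.2.1 summarises it for the on-study group only.

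One limit remains. The schedule does not collect height during follow-up, and skeletal dysplasia is part of the disease (Protocol 3.1.4.2). Weight-for-age therefore cannot separate poor nutrition from short stature. It would show that a child has left the expected course, but not why.
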